**Table 5-2 Mapping of dosing frequency to NSAID score**

Frequency	Scores	Database entry
Patient did not take any NSAID during the period of interest	0/7	
<1 day/week	0.5/7	Q2W, MISSING, PRN, UNK, ASNEEDED, QM, Q4W, Q3W
≥1 – <3 days/week	2/7	Q1W, WEEKLY, BIW
≥3 – <5 days/week	4/7	TIW, QIW
≥5 – <7 days/week	6/7	
Everyday	7/7	TID, BID, DAILY, Q24H, QID, QD
Note: Q2W=every 2 weeks, PRN=as needed, UNK=unknown, Q1W=one a week, BIW=twice a week, TIW=three times a week, TID=three times a day, BID=twice a day, QIW= four times a week, Q24H=QID=QD=one a day, QM=one a month; Q4W=one every 4 weeks; Q3W=one every 3 weeks.		

To calculate the NSAID cumulative score the following formula will be used for each NSAID being taken:

$100 * (\text{Daily dose} / \text{pre-specified max dose}) * \text{frequency score} * (\text{min}(\text{medication end date, period end date}) - \text{max}(\text{medication start date, period start date}) + 1 = \text{range of days patient used the medication}) / \text{number of days the patient was in the period.}$

In case a patient takes more than one type of NSAID, changes the dose or the frequency of NSAID during the period of interest, additional scores will be calculated for each new combination and the final score for that patient is the sum of all scores.

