From Week 16 on, those patients originally randomized to placebo will self-inject Secukinumab 150 mg at weeks 17, 18, 19 and 20, while patients originally randomized to either of the Secukinumab groups will receive their next Secukinumab injection after Week 16 at Week 20 with Placebo injections at weeks 17, 18, 19 to maintain the blinding of the treatment assignment for the secondary / exploratory endpoint analyses.

Patients will be asked to capture NSAID intake and level of AS neck, back and hip pain (BASDAI question 2; see Appendix 4) on a daily basis in a patient diary. Guidance will be

provided to patients that NSAID intake should be reduced upon an improvement in back pain and that the reduction should preferably happen step-wise and instead of an abrupt stop of any NSAID intake. However, deviance from this guidance will be acceptable and may be discussed between investigator and patient. Patients may deviate from this guidance if required, e.g. NSAID use necessary for non-spinal pain (e.g. entheses, peripheral joints, and headache). Also, if pain levels increase, patients may increase NSAID usage on an on-demand basis. The reduction in NSAID intake will be assessed using the ASAS-NSAID score (Dougados et al 2012).

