Intra-articular corticosteroids are not permitted within the 4 weeks preceding randomization and up to Week 12. After Week 12, no more than 1 joint per 24-week period may be injected. No single injection should exceed 40 mg of triamcinolone (or equivalent) and the total dose of intra-articular corticosteroid may not exceed 80 mg of triamcinolone (or equivalent) during any 20-week period. Injection of intra-articular steroids is not permitted within 8 weeks prior to Week 20.

Non-steroidal anti-inflammatory drugs (NSAIDs) (including COX-1 or COX-2 inhibitors), low strength opioids and acetaminophen/paracetamol

Patients regularly using NSAIDs, low strength opioids, or paracetamol/acetaminophen should be on stable dose for at least 2 weeks before randomization to allow inclusion. They should remain on a stable dose in the study up to Week 4.

Changes in the NSAID intake will be captured by the patient in the patient diary and checked and be transferred into the eCRF at all scheduled study visits after week 4.

Patients taking low strength opioids or paracetamol/acetaminophen PRN within the 2 weeks before randomization can continue to do so in the study; however, they have to refrain from any intake during at least 24 hours before a visit with disease activity assessment.

After Week 12 assessments are completed, a change in the low strength opioids, or paracetamol/acetaminophen treatment regimen is permitted.

Any change of the low strength opioids, or paracetamol/acetaminophen treatment during the trial should be recorded on the appropriate Prior and Concomitant medication eCRF page.

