Week	-10 to -4	-4 to -2	BSL	1	2	3	4	5	6	7	8	12	16	17	18	19	20	F24
Adverse events/SAEs (if applicable, including injection site reactions) ⁷	X																	
NSAID intake reported in eCRF		Χ	Х	Х	Х	Х	Х											X
Provide NSAID Diary to patient and instruct patient							Х				Х	х	Х					
NSAID intake captured in patient diary								х	х	Х	Х	х	Х	х	Х	х	Х	
Check NSAID diary									Х		Х	Х	Χ				Χ	
Patient's global assessment of disease activity (VAS)			x	х	X		x		x		X	X	X				X	х
Patient's assessment of back pain intensity (VAS)			х	х	х		х		Х		Х	х	Х				Х	х
BASFI			Х	Х	Х		Х		Х		Х	Х	Х				Х	Х

	Scree	ning ¹																
	Screening Visit 1	Screening Visit 2		Treatment 1										Follow Up				
Week	-10 to -4	-4 to -2	BSL	1	2	3	4	5	6	7	8	12	16	17	18	19	20	F24
BASDAI			Х	Х	Х		Х		Х		Х	Х	Х				Х	Х
Spinal mobility (BASMI Linear + chest expansion)			х		Х		х				х	х	х				Х	
SF-36			Х				Х					Х					Х	
ASAS Health Index			Х				Х					Х					Х	
Erythrocyte Sedimentation Rate (ESR)		Х	х		Х		х				Х	х	х				Х	х
High sensitivity C-reactive protein (hsCRP)		Х	х		Х		Х				х	х	х				Х	х
HLA-B27			Х															

¹ If the patient's washout period ≤ 4 weeks, Screening visit 1 (SV1) and Screening visit 2 (SV2) can be performed on the same day.

² Eligibility and relevant medical history assessments are conducted at SV1, SV2 and Baseline (BSL) / Day 1'. The data for all three visits should be recorded on the corresponding eCRFs available at SV1.

³ The following eCRFs are to be completed: AS Disease background eCRF, Modified New York criteria for AS eCRF

⁴ These assessments are source documentation only and will not be entered into the eCRF.

⁵ The PPD skin test can be performed at any time during the Screening period, but it must be read within 72 hours and before randomization.

	Scree	ening ¹																
	Screening Visit 1	Screening Visit 2					Treat	tment	:1					Tre	eatment	2		Follow Up
Week	-10 to -4	-4 to -2	BSL	1	2	3	4	5	6	7	8	12	16	17	18	19	20	F24

⁶ A chest X-ray or MRI is required if it was not performed and evaluated within 3 months prior to Screening. The X-ray should be performed after it is certain the patient meets inclusion/exclusion criteria in order to minimize unnecessary exposure to radiation. The X-ray may be replaced by an MRI assessment.

⁷ AEs/SAEs occurring after the patient has signed the informed consent must be captured on the appropriate eCRF page. SAEs must be recorded from signing of informed consent, AEs must be captured from the BSL visit on.

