### 5.5.7 ASAS-NSAID Score

The recommendations by ASAS (Dougados 2010) will be used to score each patient's NSAID use during specific time periods. The components that go into the calculation of the score is the type of NSAID, average daily dose, length in days of the time period of interest and the number of days with NSAID intake within the time period of interest. The final score should be between 0 and 100 but can in rare cases be larger than 100.

The scoring of NSAIDs is described below.

Score	Intake
0	No intake
100	150 mg diclofenac, 600 mg etodolac, 150 mg indometacin, 20 mg piroxicam, 1000 mg naproxen, 90 mg etoricoxib, 200 mg ketoprofen, 20 mg tenoxicam, 200 mg aceclofenac, 200 mg flurbiprofen, 15 mg meloxicam, 400 mg celecoxib, 2400 mg ibuprofen, 400 mg phenylbutazone.

The CRF provided dose information will be handled as follows:

- Doses > maximum dose will be scored as > 100
- Missing doses will be scored with maximum daily dose for the current NSAID (i.e. score of 100)

Drug start and end dates are needed in order to know the number of days an NSAID was prescribed. In case they are missing, the following rules will be used:

- Missing start dates will assume the start date of medication is Day -28 (i.e. prior to start of study drug)
- Missing end dates will assume the end date of medication is the patient's last day in the Study

- If the study drug is ongoing when the patient discontinues then the drug end date will be equal to the day of discontinuation. The period end date will also end on the day of discontinuation

The table below presents the score associated with the dosing frequency as specified by the ASAS definition and how the different database entries will be categorized. The frequency was not consistently specified in the ASAS publication, the below categorization was selected.

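### If NSAID records after Week 4 are coded as-needed, unknown or missing, the 0.5/7 in SAP Table 5-2 misstates the ASAS-NSAID score behind H2, H7 and H8

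*SAP*

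**What the plan says.** **SAP.** Section 5.5.7 lists what goes into the score, including "the number of days with NSAID intake within the time period of interest". The formula that follows is 100 × (daily dose / maximum dose) × frequency score × (days of the record's date range inside the period) / (days the patient was in the period). It describes that date range as the "range of days patient used the medication". Table 5-2 turns database codes into the frequency score. Its lowest non-zero row, for under 1 day a week, is worth 0.5/7 and holds "Q2W, MISSING, PRN, UNK, ASNEEDED, QM, Q4W, Q3W". The stated reason for the table is: "The frequency was not consistently specified in the ASAS publication, the below categorization was selected". A missing dose is scored at the maximum, and a missing end date runs to the patient's last day in the study. Section 5.5.7 does not name the diary; elsewhere the SAP mentions it only as the source of reasons for not tapering. SAP section 4 declares no change to the protocol's analyses.

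**Protocol.** Section 3.1 allows on-demand NSAID use and has intake recorded "on a daily basis in a patient diary". Section 5.5.7 says: "Changes in the NSAID intake will be captured by the patient in the patient diary and checked and be transferred into the eCRF", at scheduled visits after Week 4. Section 8.3 has site staff enter the paper diary into the eCRF. In Table 6-1 the row "NSAID intake reported in eCRF" is marked at Screening 2, baseline, Weeks 1 to 4 and F24; the row "NSAID intake captured in patient diary" is marked from Week 5 to Week 20. Section 6.4.1 builds the score from daily dose and the proportion of days on which NSAIDs are taken. Section 13.4.1 turns to frequency categories when the exact day count is not known, which it says is usual when visits are more than 2 weeks apart.

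**The concern.** Entry requires regular intake at 50% or more of the highest recommended dose (Protocol 4.1, criterion 8), and on-demand use is allowed once tapering starts. As-needed coding is therefore most plausible in the period that the Week 12 score measures. A patient still taking NSAIDs several days a week, but coded as needed, would look as if intake had almost stopped.

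The SAP's reason for Table 5-2 speaks to where the category boundaries lie. It does not explain why unknown or on-demand intake should count as half a day a week. The missing-data rules also pull in opposite directions without explanation: a missing dose gets the highest value, a missing frequency the lowest non-zero one.

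H2, H7 and H8 all test change in this score at Week 12. H2 is second in the testing sequence, and if it fails, H3 to H11 become exploratory (SAP 2.7.2).

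**Working it through.** **1. The plan's own figures.** The worked example in Protocol 13.4.1 reproduces: 100 × 120 × (4/7) / 180 = 38.1 and 50 × 60 × (2/7) / 180 = 4.8, total 42.9. Protocol 9.7 assumes reductions of 63.9 and 36.6, a difference of 27.3, with SD 40. With 62 per group at two-sided 5%, power for one secukinumab arm against placebo is 96.7%, in line with the stated >90%.

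**2. Score of a coded record.** Let f be the dose as a fraction of the maximum and d the true days of intake per week, for a record spanning the whole period with dose and dates present.
- SAP score = 100 × f × 0.5/7, which is 7.1 at full dose and 3.6 at half dose, whatever d is.
- Score from actual days = 100 × f × d/7.
- Error = 100 × f × (0.5 − d)/7, which is zero at exactly d = 0.5.

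| True days/week | Error, full dose | Error, half dose |
|---|---|---|
| 0 | +7.1 | +3.6 |
| 0.5 | 0 | 0 |
| 2 | −21.4 | −10.7 |
| 3 | −35.7 | −17.9 |
| 4 | −50.0 | −25.0 |

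**3. The same intake under two codings.** Full dose on 12 of 28 days scores 100 × 12/28 = 42.9 if entered as dated daily records, and 7.1 if entered as one as-needed record. The gap is 35.7.

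**4. Offsets inside the SAP.** If the dose is missing it is scored at 100, so a patient truly on half dose breaks even at 1 day a week (50 × 1/7 = 7.1) and one on quarter dose at 2. A missing end date lengthens the range: true use of 0.8 day a week on 14 of 28 days is 100 × (0.8/7) × 14/28 = 5.7, against a scored 7.1.

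**5. Effect on the arm comparison (illustration; the shares are assumed).** Suppose placebo has 10 percentage points more of these records than secukinumab, with true use of 4 days a week and SD unchanged. The contrast loses 0.10 × 50.0 = 5.0 points at full dose, or 2.5 at half dose. Take 190 patients as 127 against 63.
- H2: SE = 40 × √(1/127 + 1/63) = 6.16. Power goes from 99.3% to 95.1% (half dose 98.0%).
- H7 and H8: SE = 40 × √(2/63) = 7.13. Power goes from 96.9% to 87.9% (half dose 93.6%).

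The same excess in the secukinumab arms would enlarge the apparent effect by the same 5.0 or 2.5 points. Equal shares with equal use give zero.

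**The case against.** The strongest reply is that no defect in the actual scores has been shown. Diary intake is transferred to the eCRF, SAP 5.5.7 works from CRF data, and each change of dose or frequency is scored separately and summed. If diary days arrive as dated daily entries, the formula already counts days. This stands. A reader might infer that the SAP discards the diary; the documents show only that 5.5.7 does not name it. They give neither the eCRF layout nor the number of records with these codes.

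The formula also has the same form as the one in Protocol 13.4.1, and that section expects category scoring when visits are more than 2 weeks apart, as Weeks 8 and 12 are. That is fair as far as it goes. But long visit gaps are given as the usual reason for not knowing the days, and here a daily diary can supply them. Nor does 13.4.1 give any value to unknown or as-needed intake.

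The category edges differ between the two documents, and a reader might take that as further bias. It is not shown to be. At exactly 3 days a week and full dose, actual days give 42.9, the SAP 57.1 and the protocol text 28.6, so each is about 14.3 off. At 1 day a week (actual 14.3) the SAP gives 28.6 and the protocol 7.1. The protocol's own example also labels its bands loosely. These are two conventions, and the difference only needs recording.

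Finally, a day-count rule can itself mislead. If patients write only on intake days, 8 intake days and 20 blanks divided by days with entries scores 100 instead of 100 × 8/28 = 28.6. This stands and shapes the remedy.

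**Conclusion.** The concern holds conditionally. If records after Week 4 carry the as-needed, unknown or missing codes rather than dated daily entries, and dose and dates are recorded, Table 5-2 understates the score when true use exceeds 0.5 day a week and overstates it below that. At full dose and 3 days a week the error in a single record, 35.7 points, exceeds the planned mean difference of 27.3; at half dose it is 17.9.

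It is tempting to conclude that the rule exaggerates the NSAID-sparing effect of secukinumab. The documents do not support that: the shares of these codes by arm are not given, so the bias may go either way or cancel, and missing doses or end dates can offset it. H1 is unaffected. The SAP should be changed before lock. Confidence is medium, because the coding of diary days is unknown.

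**What to change.** Before database lock:

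1. In SAP 5.5.7, where day-level diary data are in the eCRF, replace the whole product of frequency score and date range over days in period by (days with intake of that NSAID and dose) / (days in the period). Part-period use is then discounted once: full dose daily on 14 of 28 days gives 50, as now. Fix the handling of blank diary days in advance from the diary instructions: no intake if patients record only intake days, otherwise missing. Run the other reading as a sensitivity analysis and report blank days by arm.
2. Use Table 5-2 only where day counts are unavailable.
3. Keep 0.5/7 as the fallback for PRN, ASNEEDED, UNK and MISSING, and repeat H2, H7 and H8 with higher values, for example 4/7, and 7/7 as an upper bound.
4. Tabulate, blinded, the number of records with these codes by visit period. This shows whether the problem arises.
5. Record in SAP section 4 that the category edges and the handling of these codes differ from Protocol 13.4.1, without presenting the edge differences as bias.

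If the eCRF holds only frequency codes, steps 3 to 5 apply.

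The cost is SAP wording, some derivation programming, one blinded table and a few sensitivity runs. Step 1 needs no new data if day-level entries are already in the eCRF. Going back to the paper diaries is not asked for.

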## **5.6 Rule of exclusion criteria of analysis sets**

Deviation ID	Description of Deviation	Exclusion in Analyses	Severity code
INCL01	Patients have not signed Informed Consent Form prior to initiation of any studyrelated procedure	INCLUDE IN EVERYTHING	0
INCL02a	Age criteria not met	INCLUDE IN EVERYTHING	0
INCL02b	Pregnant or Lactating female patients	INCLUDE IN EVERYTHING	0
INCL03	Are modified New York Criteria for Ankylosing Spondylitis fulfilled or met Is No in Modified New York criteria form	INCLUDE IN EVERYTHING	0
INCL04	BASDAI Average Score less than 4 at baseline	INCLUDE IN EVERYTHING	0
INCL05	BASDAI Question 2 is less than 4 cm at baseline	INCLUDE IN EVERYTHING	0
INCL06	Total back pain is less than 40 mm at baseline	INCLUDE IN EVERYTHING	0
INCL07	Patient is not on at least 2 different NSAIDs at the highest recommended dose for at least 4 weeks in total in the past, prior to randomization	INCLUDE IN EVERYTHING	0
INCL08a	Patient has not reported regular intake of NSAIDs of at least 50 percent of the highest recommended dose at Screening	INCLUDE IN EVERYTHING	0
INCL08b	Patient with prior TNF $\alpha$ inhibitor therapy has not reported regular intake of NSAIDs of at least 50 percent of the highest recommended dose at baseline after the appropriate washout.	INCLUDE IN EVERYTHING	0
INCL09	Patient is not on a stable dose of NSAIDs for at least 2 weeks before randomization.	INCLUDE IN EVERYTHING	0
INCL10	Patient has previously been on a TNF alpha inhibitor however, an appropriate washout period was not maintained prior to randomization	INCLUDE IN EVERYTHING	0
INCL11	Pt on TNF alpha I and not exprncd inadequate response to previous or current trtmnt at approved dose for at least 3M prior to Rndz or not intolerant to at least 1 administration of anti TNF alpha	INCLUDE IN EVERYTHING	0
INCL11a	patients that did not tolerate TNF alpha inhibitor or that were inadequate responder are eligible for study however the reason for discontinuation is equal other in Concomitant medication CRF	INCLUDE IN EVERYTHING	0
INCL12	If a patient taking MTX or sulfasalazine continues taking, but either took MTX prevoisly for shorter than 3 Months or the	INCLUDE IN EVERYTHING	0

	dose was not stable in the last 4 week prior to randomization		
INCL13	Patient on MTX is not on stable folic acid supplementation before randomization	INCLUDE IN EVERYTHING	0
INCL14	Patient has not discontinued DMARD 4 weeks prior to randomization	INCLUDE IN EVERYTHING	0
INCL15	Patients taking systemic corticosteroids have to be on a stable dose	INCLUDE IN EVERYTHING	0
EXCL01	Chest Xray or MRI with evidence of ongoing infectious or malignant process, obtained within 3 months of screening and evaluated by a qualified physician	INCLUDE IN EVERYTHING	0
EXCL02	Patients taking high potency opioid analgesics eg methadone hydromorphone and morphine	INCLUDE IN EVERYTHING	0
EXCL03	Previous exposure to Secukinumab or any other biologic drug directly targeting IL17 or IL17 receptor	INCLUDE IN EVERYTHING	0
EXCL04	Use of any IND and or devices within 4W of RNDMZ or period of 5 halfives of investigational drug or participation in another study in the same indication during enrollment in this study	INCLUDE IN EVERYTHING	0
EXCL05	History of hypersensitivity to the study drug or its excipients or to drugs of similar chemical classes	INCLUDE IN EVERYTHING	0
EXCL06	Any therapy by intraarticular injections example corticosteroid within 4 weeks before randomization	INCLUDE IN EVERYTHING	0
EXCL07	Any intramuscular corticosteroid injection within 2 weeks before randomization	INCLUDE IN EVERYTHING	0
EXCL08	Patients previously treated with any biological immunomodulating agents except those targeting TNF alpha	INCLUDE IN EVERYTHING	0
EXCL09	Patients who have taken more than two anti TNF alpha agents	INCLUDE IN EVERYTHING	0
EXCL10	Previous treatment with any cell depleting therapies including but not limited to anti CD20 or investigational agents example CAMPATH anti-D4 antiCD5 antiCD3 antiCD19	INCLUDE IN EVERYTHING	0
EXCL11	Pregnant or nursing lactating women where pregnancy is defined as the state of a female after conception and until the termination of gestation, confirmed by a positive hCG laboratory test	INCLUDE IN EVERYTHING	0
EXCL12	Women of childbearing potential not using effective contraception methods during entire study or longer if required by locally approved prescribing info	INCLUDE IN EVERYTHING	0
EXCL13	Active ongoing inflammatory diseases other than AS that might confound the evaluation of	INCLUDE IN EVERYTHING	0

	the benefit of Secukinumab therapy, including inflammatory bowel disease or uveitis		
EXCL14	Underlying conditions which in the opinion of the investigator immunocompromises the patient and or places the patient at unacceptable risk for participation in an immunomodulatory therapy	INCLUDE IN EVERYTHING	0
EXCL15	Significant medical problems or diseases or very poor functional status unable to perform self care	INCLUDE IN EVERYTHING	0
EXCL16	History of clinically significant liver disease or liver injury as indicated by abnormal liver function tests such as SGOT AST and SGPT ALT alkaline phosphatase or serum bilirubin	INCLUDE IN EVERYTHING	0
EXCL17	History of renal trauma glomerulonephritis or patients with one kidney only or a serum creatinine level exceeding 1.5 milligram per decilitre 132.6 micromol per litre	INCLUDE IN EVERYTHING	0
EXCL18	Screening total WBC count less than 3000 per micro litre or platelets less than 100000 per microlitre or neutrophils less than 1500 per micro litre or hemoglobin less than 85 gram per litre	INCLUDE IN EVERYTHING	0
EXCL19	Active systemic infections during the last two weeks prior to randomization exception: common cold	INCLUDE IN EVERYTHING	0
EXCL20a	History of ongoing, chronic or recurrent infectious disease or evidence of tuberculosis infection.	INCLUDE IN EVERYTHING	0
EXCL20b	History of ongoing, chronic or recurrent infectious disease or evidence of tuberculosis infection	INCLUDE IN EVERYTHING	0
EXCL21	Known infection with human immunodeficiency virus HIV hepatitis B or hepatitis C at screening or randomization	INCLUDE IN EVERYTHING	0
EXCL22	History of lymphoproliferative disease or any known malignancy or history of malignancy of any organ system within the past 5 years	INCLUDE IN EVERYTHING	0
EXCL23	Current severe progressive or uncontrolled disease which in the judgment of the clinical investigator renders the patient unsuitable for the trial	INCLUDE IN EVERYTHING	0
EXCL24	Inability or unwillingness to undergo repeated venipuncture Example because of poor tolerability or lack of access to veins	INCLUDE IN EVERYTHING	0
EXCL25	Inability or unwillingness to receive injections with PFS	INCLUDE IN EVERYTHING	0
EXCL26	Any medical or psychiatric condition which in the Investigators opinion, would preclude the	INCLUDE IN EVERYTHING	0

	participant from adhering to the protocol or completing the study per protocol		
EXCL27	Donation or loss of 400 mL or more of blood within 8 weeks before dosing	INCLUDE IN EVERYTHING	0
EXCL28	History or evidence of ongoing alcohol or drug abuse, within the last six months before randomization	INCLUDE IN EVERYTHING	0
EXCL29	Plans for administration of live vaccines during the study period or 6 weeks prior to randomization	INCLUDE IN EVERYTHING	0
EXCL30	Patients who are intolerant to NSAIDs	INCLUDE IN EVERYTHING	0
COMD01	Concomitant use of Etanercept during the study	INCLUDE IN EVERYTHING	0
COMD02	Concomitant use of Infliximab during the study	INCLUDE IN EVERYTHING	0
COMD03	Concomitant use of following medications during the study  Adalimumab golimumab certolizumab	INCLUDE IN EVERYTHING	0
COMD04	Concomitant use of Leflunomide during the study	INCLUDE IN EVERYTHING	0
COMD05	Systemic corticosteroids use within 2 weeks prior to Baseline	INCLUDE IN EVERYTHING	0
COMD06	Intra articular steroids injections use during the study	INCLUDE IN EVERYTHING	0
COMD07	MTX dose is changed between BL and W12 for reason other than an AE	INCLUDE IN EVERYTHING	0
COMD08	Patient taking MTX do not take folic acid supplementation during the study	INCLUDE IN EVERYTHING	0
COMD09	The corticosteroid dose reduced by more than 1 mg prednisone equivalent every 4 weeks	INCLUDE IN EVERYTHING	0
COMD10	Pts regularly using NSAIDs low strength opioids paracetamol acetaminophen not on stable dose for at least 2W before randomization to allow inclusion Or not on a stable dose in the study up to W4	INCLUDE IN EVERYTHING	0
COMD11	Live vaccines less than 6 weeks before randomization or  Live vaccines given before 12 weeks after last study treatment administration.	INCLUDE IN EVERYTHING	0
COMD12	Incorrect study medication given OR additional study medication given	INCLUDE IN EVERYTHING	0
COMD13	Patient not discontinued study drug despite severe or serious AE that is not compatible with administration of study medication	INCLUDE IN EVERYTHING	0

COMD14	Concomitant use of Systemic corticosteroids greater than 10mg prednisone equivalent	INCLUDE IN EVERYTHING	0
COMD15	No Unstable dose of MTX other DMARD Any investigational treatment or participation in any interventional trial & Analgesics other than paracetamol/acetaminophen or low strength opioids PRN	INCLUDE IN EVERYTHING	0
TRT01	Incorrect, missed or partial doses of study medication administered	INCLUDE IN EVERYTHING	0
OTHR01	Urinalysis not performed.	INCLUDE IN EVERYTHING	0
OTHR02	Physical examination not performed.	INCLUDE IN EVERYTHING	0
TRT02	Intake of low strength opioids is reported 24 hours before a visit with disease activity.	INCLUDE IN EVERYTHING	0
TRT03	Mishandling of investigational product.	INCLUDE IN EVERYTHING	0
TRT04	During intermediate storage of IMP no Tmin/Tmax data available. According to decision of Novartis QP medication should not be used, but was already dispensed to patient.	INCLUDE IN EVERYTHING	0
TRT05	Time frame between 2 IMP injections not respected.	INCLUDE IN EVERYTHING	0
OTHR03	Patient is outside the recommended visit window, not followed as per protocol.	INCLUDE IN EVERYTHING	0
OTHR04	ECG was not performed as per assessment schedule.	INCLUDE IN EVERYTHING	0

